4.7 Software

All analyses will be conducted using SAS® version 9.2 or later.

5. Evaluation of Demographic and Baseline Characteristics

5.1 Subject enrolment and disposition

A screened subject is a subject who has completed the activities at the Screening Visit (-28 to 0 days before day 1 cycle 1), met the inclusion and exclusion criteria, and signed the Informed Consent Form. Summary of the number of subjects in the ITT, PP and Safety sets will be provided for the dose escalation part of the study. The number and percentage of subjects who withdrew from the study and the reasons for early study termination will be summarized for the dose escalation part of the study.

5.2 Protocol violations

The classification of major and minor protocol deviations and the resulting definition of analysis sets will be performed at the end of the study by the clinical study team and assessed as “minor” or “major” in consultation with the Sponsor. Major protocol deviations are defined as those deviations from the protocol likely to have an impact on the perceived safety and tolerability of study treatments.

Forms				
Title		Statistical Analysis Plan Template		
Code		Version	Effective Date	Page
FRM_ST03_032		01	23 Apr 2015	16 of 24

A summary of all randomized subjects with at least one minor or major protocol deviation will be summarized in number and percentage by type of deviation and treatment group. A by-subject listing of major protocol deviations will also be provided.

5.3 Study discontinuations

As it is stated on section 3.4 of study protocol: if a patient is withdrawn from the study for reasons other than a DLT-associated event before the end of cycle 1 during the dose escalation portion of the study, the patient will be replaced; whereas patients who withdraw from the study or discontinue treatment after completion of cycle 1 will not be replaced.

The number of subject withdrawals and the number of subjects completing the study will be summarized. This summary will include the reasons for discontinuation.

5.4 Demographics and baseline characteristics

The subjects enrolled in the study will be statistically characterized for baseline, demographic and clinical characteristics using descriptive statistics (mean, median, standard deviation, etc.) for continuous factors such as, but not limited to, age body mass index (BMI), and by frequency and percentage distributions for categorical factors such as, but not limited to gender, race.

All summaries of continuous characteristics will be based on non-missing observations; in addition the number of missing observation will be shown. For categorical characteristics, percentages will be calculated out of the total number of subjects in the data set (i.e., each denominator includes the number of subjects with missing/unknown values for the characteristic such as but not limited to race, gender, ECOG PS etc.).

Baseline characteristic include:

- Medical history
- Concomitant medication
- ECOG Performance Status
- Full physical examination (including height and weight)
- Vital signs
- ECG (resting 12-lead)
- Clinical Chemistry (include HBV & HCV testing at Screening)
- Haematology
- Coagulation
- Urinalysis
- Tumour assessment prostate

5.5 Medical and surgical history

Medical history

Forms				
Title		Statistical Analysis Plan Template		
Code		Version	Effective Date	Page
FRM_ST03_032		01	23 Apr 2015	17 of 24

A disease is considered as medical history if it is not ongoing at screening visit (“ongoing” box is not ticked).

Concomitant disease

A disease is considered as concomitant disease if it is ongoing at screening visit (“ongoing” box is ticked).

Medical history and/or concomitant diseases will be summarised by system organ class (SOC) and preferred term (PT) using the MedDRA system (version 17.0).

Study cancer history information, as collected in the related CRF form, will be listed only.

5.6 Prior and concomitant medications

The medication documented on the concomitant medication page will be analyzed as follows:

- Prior medication, if the last intake was prior to day of first medication intake,
- Concomitant medication, if the intake was between day of first medication intake and study termination.

If the day or month of the start date is unknown, the medication will be analyzed using the available information. If this information is not sufficient for the division into one of the above mentioned categories, the worst case will be used (e.g. start date = NK/05/2015, end date = 13/05/2015, date of termination = 12/05/2015 → concomitant medication).

The analysis will be performed using the preferred name (WHO Drug Dictionary 2015). The levels used will be “Anatomical Therapeutical Chemical Classification” (ATC) and “Medication product Name” (MP).

Study cancer therapies as collected in the dedicated CRF form will be listed only.

5.7 ECOG Performance Status

Eastern Co-operative Oncology Group (ECOG) Performance Status is performed at the screening and at day 1 of cycle 2 to cycle 6 before administration of the test drug. Descriptive statistics of the ECOG PS grade will be provided by screening and by cycle (cycle 2 – 6).

5.8 Physical Examination

Full physical examination (including height and weight) will be performed at screening and at day 1, day 8 and day 15 of each cycle. Clinically significant abnormalities in physical examination will be recorded as adverse event (AE). Physical examination will be listed by phase (dose escalation phase), by cycle and time point. In addition, height and weight will also be listed.

Forms			
Title		Statistical Analysis Plan Template	
Code		Version	Effective Date
FRM_ST03_032		01	23 Apr 2015
		18 of 24	

5.9 Vital Signs

Vital signs (Systolic Blood Pressure [SBP], Diastolic Blood Pressure [DBP], Heart Rate [HR], Respiratory Rate [RR] and body temperature) will be assessed at screening, and depending on the cohorts, as follows:

- For cohorts 1, 2, 3, 4 and 6 vital signs will be assessed at day 1 cycle 1 before the administration of the test drug and up to 1 hour after the administration of the test drug and at dosing days of each cycle (day 1, day 8, day 15) before administration of the test drug;
- For cohort 5 vital signs will be assessed at day 1 cycle 1 and at day 1 cycle 4 before the administration of the test drug and up to 1 hour after the administration of the test drug and at dosing days of each cycle (day 1, day 8, day 15) before administration of the test drug;

In case of multiple assessments done in the same visit/time point, the average of the values will be calculated and used for the analysis. All assessments will be included in subject data listings.

Listings will be provided and summary of the data will be tabulated by cycle.

5.10 ECG (resting 12-lead)

The electrocardiogram (resting 12-lead) will be assessed in triplicate at the screening, at day 1 of each cycle before administration of the test drug and 1 hour (+/- 15 mins) after administration of the test drug. A listing of the following parameter will be presented for each patient: 12-lead electrocardiogram (ECG) parameters: Heart rate, PR interval, QRS duration, QTc interval, QTcF interval.

5.11 Clinical Chemistry (include HBV & HCV testing at Screening), Haematology, Coagulation and Urinalysis

Laboratory parameters will be assessed at screening, day 1, day 8 and day 15 of each cycle; except for the Urinalysis which will be assessed at screening and day 1 of each cycle. Data will be listed for dose escalation phase by dose group where applicable and cycle. In addition, descriptive statistics, with respect to the investigator's interpretation (Normal, NCS = Abnormal Not Clinically Significant, CS = Abnormal Clinically Significant, NR = No Result), will be presented by cycle and time point.

In case of multiple assessments done in the same visit/time point, the latest one (looking at date and time recorded) will be used for the analysis; in case of missing assessment time, preference will be given to assessments on same date but with time information available. All assessments will be included in subject data listings.

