4.1 General

Results for dose-escalation phase will be listed and summarized using descriptive statistics. An exact 95% CI will be calculated for the response rate observed in dose escalation phase.

Descriptive summaries of continuous variables in terms of observed values will be provided. These summaries will contain arithmetic mean, SD, minimum, median and maximum or geometric mean and %CV in place of the arithmetic mean and SD for data requiring log transform due to known skewness (e.g. PSA).

Descriptive summaries of categorical variables will consist of frequencies and percentages.

All statistical analysis (i.e.: both efficacy and safety) will be done according to the actual treatment received due to the protocol's flexibility in allowing the cohort review committee to adjust the dose of individual patients. The most frequent dose taken by a subject during all treatment occasions in each cycle will be used for subject assignment to each treatment (dose) group for the purpose of the analysis; this is to cover any dosing subjects may have received by mistake occasionally only.

Any unscheduled visits will not be used for summary tables, but listed only.

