4.4 Handling of missing and incomplete data

Missing values will be included in the denominator count when computing percentages. Only the non-missing values will be evaluated for computing summary statistics. AEs that have missing onset dates will be considered to be treatment-emergent, unless the stop date is known to be prior to the first administration of VAL201.

In order to calculate the duration of tumor, the following rules will be applied for partial dates of histological/cytological diagnosis:

- if only the day is missing, the 15th of the month will be assumed;
- if the day and the month are missing, 30th June will be assumed.

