TABLE 14.3.4-3.1.2	LABORATORY PARAMETERS: HAEMATOLOGY AND COAGULATION BY CYCLE AND TIME POINTS / INTENT TO TREAT POPULATION
TABLE 14.3.4-3.1.3	LABORATORY PARAMETERS: URINALYSIS BY CYCLE AND TIME POINTS / INTENT TO TREAT POPULATION
TABLE 14.3.4-3.2.1	LABORATORY PARAMETERS: CLINICAL CHEMISTRY BY CYCLE AND TIME POINTS / PER PROTOCOL POPULATION
TABLE 14.3.4-3.2.2	LABORATORY PARAMETERS: HAEMATOLOGY AND COAGULATION BY CYCLE AND TIME POINTS / PER PROTOCOL POPULATION
TABLE 14.3.4-3.2.3	LABORATORY PARAMETERS: URINALYSIS BY CYCLE AND TIME POINTS / PER PROTOCOL POPULATION

7.2.2 Listings:

LISTING 16.2.1-1	DISPOSITION OF PATIENTS / ALL PATIENTS
LISTING 16.2.2-1	PROTOCOL DEVIATIONS / INTENT TO TREAT POPULATION
LISTING 16.2.3-1	DEMOGRAPHIC AND BASELINE CHARACTERISTICS / INTENT TO TREAT POPULATION
LISTING 16.2.4-1	PHYSICAL EXAMINATIONS / INTENT TO TREAT POPULATION
LISTING 16.2.4-2	PAST-CONCOMITANT DISEASES / INTENT TO TREAT POPULATION
LISTING 16.2.4-3	STUDY CANCER HISTORY / INTENT TO TREAT POPULATION
LISTING 16.2.4-4	TUMOUR ASSESSMENT / INTENT TO TREAT POPULATION
LISTING 16.2.5-1	MEDICATIONS / INTENT TO TREAT POPULATION
LISTING 16.2.6-1	PROSTATE SPECIFIC ANTIGEN (PSA) / INTENT TO TREAT POPULATION
LISTING 16.2.6-2	OTHER SOLID TUMOUR / INTENT TO TREAT POPULATION
LISTING 16.2.7-1	PRE-TREATMENT ADVERSE EVENTS / INTENT TO TREAT POPULATION
LISTING 16.2.7-2.1	TREATMENT-EMERGENT ADVERSE EVENTS / SAFETY POPULATION
LISTING 16.2.7-2.2	SERIOUS TREATMENT-EMERGENT ADVERSE EVENTS / SAFETY POPULATION
LISTING 16.2.7-2.3	TREATMENT-EMERGENT ADVERSE DRUG REACTIONS / SAFETY POPULATION
LISTING 16.2.7-2.4	TREATMENT-EMERGENT ADVERSE EVENTS LEADING TO DISCONTINUATION / SAFETY POPULATION
LISTING 16.2.7-2.5	TREATMENT-EMERGENT ADVERSE EVENTS AS CODED / SAFETY POPULATION

Forms				
Title		Statistical Analysis Plan Template		
Code		Version	Effective Date	Page
FRM_ST03_032		01	23 Apr 2015	24 of 24

LISTING 16.2.8-1	VITAL SIGNS / INTENT TO TREAT POPULATION
LISTING 16.2.8-2	12-LEAD ECG / INTENT TO TREAT POPULATION
LISTING 16.2.8-3	ESTERN CO-OPERATIVE ONCOLOGY GROUP (ECOG) PERFORMANCE STATUS / INTENT TO TREAT POPULATION
LISTING 16.2.8-4.1	LABORATORY PARAMETERS: CLINICAL CHEMISTRY / INTENT TO TREAT POPULATION
LISTING 16.2.8-4.2	LABORATORY PARAMETERS: HEAMATOLOGY AND COAGULATION / INTENT TO TREAT POPULATION
LISTING 16.2.8-4.3	LABORATORY PARAMETERS: URINALYSIS / INTENT TO TREAT POPULATION
LISTING 16.2.8-6	PK PARAMETERS / PK POPULATION

7.2.3 Figures:

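### Laboratory summaries keep only the latest same-visit repeat and leave out unscheduled visits, and no worst-value table is planned, so transient clinically significant abnormalities can appear in listings only

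*SAP*

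**What the plan says.** Section 5.11 of the SAP plans laboratory assessments at screening and on Days 1, 8 and 15 of each cycle (urinalysis at screening and Day 1 only). The summary counts the investigator's interpretation in four classes: "Normal, NCS = Abnormal Not Clinically Significant, CS = Abnormal Clinically Significant, NR = No Result". It is laid out by cycle and time point.

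Four rules decide which values reach that summary and how percentages are formed:

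- **Repeats (5.11).** With several assessments at the same visit or time point, "the latest one (looking at date and time recorded) will be used for the analysis". If a time is missing, "preference will be given to assessments on same date but with time information available".
- **Unscheduled visits (4.1).** "Any unscheduled visits will not be used for summary tables, but listed only".
- **Percentages (4.4).** "Missing values will be included in the denominator count when computing percentages".
- **Continuous summaries (4.4).** "Only the non-missing values will be evaluated for computing summary statistics".

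The laboratory entries in the table list (7.2.1) all follow the by-cycle layout, for example "LABORATORY PARAMETERS: HAEMATOLOGY AND COAGULATION BY CYCLE AND TIME POINTS / INTENT TO TREAT POPULATION", with matching tables for the per-protocol set. None shows a worst on-treatment value, a CTCAE grade or a shift from baseline. Section 5.11 does put every assessment into the subject listings, and section 7.2.2 names those listings.

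**The concern.** Section 6.2.1 makes the laboratory summary part of the safety and tolerability assessment, a secondary objective. In a dose-escalation study the natural question for such a summary is whether a patient ever had a clinically significant abnormality, and at which dose. The planned tables cannot answer it. They show one retained value per scheduled time point, and two kinds of result are removed before tabulation: a value superseded by a later one at the same visit, and anything measured at an unscheduled visit.

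The adverse event tables might fill this gap, but the SAP does not say that they do. Its only statement of that kind concerns another assessment, in section 5.8: "Clinically significant abnormalities in physical examination will be recorded as adverse event (AE". Sections 5.11 and 6.2.1 have no counterpart for laboratory values. At stake is whether the report's laboratory summary gives a fair picture of transient abnormalities, or whether a reader must reconstruct it from listings.

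**Working it through.** The SAP states no figure for the effect of these rules, so there is none to reproduce. The check follows each rule through, with illustrative numbers where arithmetic helps.

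**1. What can reach a laboratory summary table**

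| Result | In a by-cycle table? | In a listing? |
|---|---|---|
| Clinically significant at a scheduled visit, no repeat | Yes | Yes |
| Clinically significant, then normal on a later repeat at the same visit | No (5.11) | Yes |
| Clinically significant at an unscheduled visit | No (4.1) | Yes |

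Section 7.2.1 has no other laboratory table, so nothing recovers the second and third rows in summary form. This step needs no assumption.

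**2. Latest-value rule: direction and possible size**

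The latest of several values can never be worse than the worst of them. Whether the rule biases the rate depends on why repeats are taken, which the SAP does not say.

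Assumed model (none of it from the SAP): true value T ~ N(0,1); first and repeat measurements are T plus independent error with SD e; a value is abnormal above 1.645 × √(1 + e²), which flags 5% of first samples. The correlation between repeats is then 1/(1 + e²). Simulation with 2,000,000 draws gives the tabulated abnormal rate:

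| e | Correlation | First value | Latest, repeat only if first abnormal | Same, with true worsening of 0.5 before the repeat | Latest, 10% repeated at random | Worst, 10% repeated at random |
|---|---|---|---|---|---|---|
| 0.3 | 0.92 | 5.0% | 3.3% | 4.7% | 5.0% | 5.2% |
| 0.5 | 0.80 | 5.0% | 2.5% | 3.8% | 5.0% | 5.3% |
| 0.8 | 0.61 | 5.0% | 1.6% | 2.5% | 5.0% | 5.3% |

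The direct bivariate normal calculation agrees. With c = 1.645, the share of abnormal first values replaced by a normal repeat is 1 − P(both > c)/0.05:

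- correlation 0.5: 1 − 0.0122/0.05 = 0.76
- correlation 0.7: 1 − 0.0196/0.05 = 0.61
- correlation 0.9: 1 − 0.0319/0.05 = 0.36

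So repeats triggered by abnormal values lower the tabulated rate. Repeats unrelated to the result leave it unchanged.

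**3. Unscheduled visits**

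For the question of any abnormal value on treatment, leaving out results can only lose findings. For the by-visit percentages actually planned, the scheduled values are untouched and the direction is not fixed: if an abnormal scheduled value is rechecked as normal at an unscheduled visit, the abnormal value stays in the table.

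**4. Missing values in the denominator**

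Let t patients have a result out of N. Every category's percentage is multiplied by t/N.

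- Assumed N = 6 with 1 clinically significant, 1 abnormal but not clinically significant, 2 normal and 2 missing: clinically significant goes from 1/4 = 25.0% to 1/6 = 16.7%; normal goes from 2/4 = 50.0% to 2/6 = 33.3%. The ratio of the two is 0.5 both times.
- Assumed N = 10 with 5 tested, 2 abnormal and 3 normal: abnormal goes from 40% to 20%; normal goes from 60% to 30%.

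Missing patients are not counted as normal, so this rule does not shift the table towards normal. Means and medians use non-missing values only and are unaffected.

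**The case against.** The strongest reply is that nothing is lost from the report. Every assessment is listed, and with cohorts of one to three patients, expandable to six, listings are a main safety display. The latest-value rule is also narrow: it covers only repeats within one visit or time point. The SAP does not say why repeats are taken, so an assumption that they follow abnormal results is the reader's own. Whether clinically significant laboratory findings are recorded as adverse events is commonly a protocol matter, and the protocol was not available for this review; treatment-emergent events are tabulated by dose, severity and causality. The illustration uses a numerical cut-off, whereas the tables count an investigator's judgement.

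Much of this stands. It limits the point to the summary tables, makes the bias conditional and rules out sizing it. It does not remove the gap: a listing is not a summary, section 6.2.1 promises both, and the SAP itself does not show that adverse event reporting covers laboratory values.

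A reader might go further and infer that the repeat, unscheduled-visit and denominator rules all push the tables towards normal, and that the maximum tolerated dose is therefore at risk. The SAP does not support that. The denominator rule shrinks normal and abnormal percentages by the same factor. Dropping unscheduled visits has no fixed direction in by-visit tables. Under section 3.5, dose-limiting toxicities rest on drug-related Grade 3 or 4 adverse events and on Cycle 1 dosing problems; under section 6.1, escalation rests on the Cohort Review Committee's review of patient safety data. Neither depends on these tables.

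**Conclusion.** The point holds in a limited form. As written, the SAP produces no laboratory summary in which a clinically significant value rechecked as normal at the same visit, or found at an unscheduled visit, can appear. That follows from sections 4.1, 5.11 and 7.2.1 alone.

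That the tabulated rate is also understated is conditional on repeats being prompted by abnormal results. The drop from 5.0% to between 1.6% and 3.3% further assumes that every abnormal first value is repeated within the same visit, a 5% cut-off and a normal error model. It shows that the effect could be material; it does not estimate it for this trial.

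The consequence is confined to the descriptive laboratory summary for a secondary objective. The primary assessment is untouched. The denominator rule calls for clearer display rather than correction of a bias: section 4.4 does not say whether patients who have left the study count as missing at later cycles, so a percentage without its number tested is hard to read.

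**What to change.** Add one table, on the safety set and by dose, giving for each patient and laboratory parameter the worst post-baseline investigator category (or CTCAE grade), taken from all scheduled, repeat and unscheduled values. State how patients whose dose changed are placed, since section 4.1 assigns the dose group by cycle. The existing by-cycle tables can stay, with the number of patients with a result shown beside each percentage.

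The values are already collected and listed, so the cost is one extra table and a small change of layout. The downside is slightly more output and somewhat less favourable percentages.

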5.12 Tumour assessment prostate

Tumour assessment for prostate cancer patients will follow the PCWG2 guidelines or RECIST 1.1 guidelines and may include assessment of serum prostate-specific antigen (PSA) at screening and every 3 weeks or at the end of every cycle.

Forms				
Title		Statistical Analysis Plan Template		
Code		Version	Effective Date	Page
FRM_ST03_032		01	23 Apr 2015	19 of 24

A summary table for tumour assessment at screening and at each applicable cycle will be produced presenting descriptive statistics for longest tumour diameter (mm) reported as well as duration of tumour (years) and method of examination; longest tumour diameter will be classified by tumour location and such categories will be defined by a study medical expert reviewing the related information collected.

The assessment of prostate-specific antigen PSA outcomes will be summarised for each patient and time point including the percent change in PSA from baseline to tumour assessment time point.

An estimate of pre-treatment PSA doubling time will be presented in a summary table together with descriptive statistics for PSA values at each cycle and the related percent change from baseline.

Baseline PSA value is defined as the last available assessment before treatment start (which will be actually the PSA value collected at Cycle 1 Day 1).

Thereafter tumour assessment and prostate-specific antigen PSA assessment results will be listed, including also maximum decline in PSA during study.

If other methods were used to assess the tumour such CT scan or MRI then the results of the tests will be listed for each patient by time point.

6. Evaluation of objectives

The evaluation of the primary objective will be based on the safety set, the evaluation of the secondary objective will be based on the ITT set and the evaluation of the exploratory objective will be based on the ITT set and the PP set separately. Tables and listings will be presented separately.

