3.1 General design and plan

This clinical study is designed to establish the MTD/MAD, safety, tolerability and PK of VAL201 by testing the drug (VAL201) on patients with incurable, locally advanced or metastatic prostate cancer and other advanced solid tumors. The design is a Phase I/II, open-label single-arm dose escalation study. The study design consists of a dose escalation part followed by an enrichment part. The study features includes: five cohorts of up to six patients, six cycles (main study) each cycle will last 21 days and an extended treatment period of VAL201 if a patient is considered suitable. Events that occur during each cycle will be considered for Dose Limiting Toxicity (DLT) assessment and therefore to establish the MTD/MAD.

The dose escalation will follow an accelerated enrolment of 3+3 design where the first two cohorts will enroll 1 patient each with an accelerated dose escalation schedule as described on Section 4.2 of the clinical study protocol (VAL201-001 version F6.0). Each patient will be followed up for AEs and DLT during each cycle. Where the Cohort Review Committee (CRC) suspects that drug-related events have occurred that merit further exploration at that dose level, they will request that the cohort 1 or 2 must enroll 3 more patients in order to thoroughly evaluate safety events prior to escalation. Cohorts of 3 patients will be enrolled from the 3rd cohort onwards (or earlier where the CRC recommend due to safety data evaluation). After a DLT has been identified the cohort will be expanded to 6 patients. If a second DLT is reported this will be declared the MTD.

The starting dose of VAL201 for the first cohort of patients will be 0.5 mg/kg/dose given on Days 1, 8 and 15 of each cycle. In the absence of DLT, the dose of VAL201 will be escalated for future cohorts in recommended increments according to the rules for dose escalation as described in Section 4.2 of clinical study protocol. All dose escalation decisions will be made by a CRC who shall convene to review all available safety data.

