3.4.1 Secondary objective assessment

- Evaluation of AEs during treatment and follow up.
- Assessment of pharmacokinetics measures.
- Tumor assessments following PCWG2 and RECIST 1.1 recommendations and may include the following as appropriate:
 - assessment of measurable and any selected non-measurable lesions by MRI scan (or CT if not possible) of chest, and abdomen/pelvis at Screening and on the completion of every 2 cycles (every 3 cycles in Cohorts 5 and 6);

Forms			
Title		Statistical Analysis Plan Template	
Code		Version	Effective Date
FRM_ST03_032		01	23 Apr 2015
		11 of 24	

- assessment of PSA levels in serum at screening and every 3 weeks (or at the end of each cycle);
- assessment of bone lesions by a whole-body radionuclide scan at Screening and on the completion of every 2-4 cycles (3 cycles in Cohorts 5 and 6);
- other assessments e.g. whole body MRI may be assessed as requested by investigator.
- percent change in PSA from baseline to tumour assessment time point;

$$\text{Percent change} = [1 - \exp(\ln(\text{PSA}_{\text{C}}/\text{PSA}_{\text{B}}))] * 100;$$

where:

PSAb is the PSA at the screening (day -28 to 0)

PSA_C is the PSA at day 1 of each cycle (x indicates the cycle 1 to 7 and onwards)

- maximum decline in PSA during study defined as the maximum reduction in PSA from the baseline (looking at all visits, following Cycle 1 Day 1, which is indeed Baseline Visit for PSA, up to the last final cycle visit or the last dosing visit, if final cycle visit is not present, inclusive); this value will be determined by the percent change in PSA from baseline, a negative percent will indicate a decline in PSA.
- based on the three pre-treatment PSA values, an estimate of pre-treatment PSA doubling time will be derived by regressing the natural log of the PSA values versus the time points, the slope of the regression will be used to estimate pre-treatment PSA doubling time

$$\ln(\text{PSA}) = a + bt_x$$

$$\text{doubling time: } \ln(2)/b$$

where \ln is the natural logarithm

a is the intercept,

b is the slope,

t_x are the time where the PSA test was performed.

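### PSA percent change has no workable group mean under the SAP's own geometric-mean rule; read literally, the arithmetic mean and SD apply, and in groups of 3 to 6 patients one large rise can dominate them

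*SAP*

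**What the plan says.** Section 4.1 sets the statistics for continuous variables. The default is: "These summaries will contain arithmetic mean, SD, minimum, median and maximum". The alternative is "geometric mean and %CV in place of the arithmetic mean and SD for data requiring log transform due to known skewness (e.g. PSA"). PSA is the only example given. Minimum, median and maximum are planned in either case.

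Section 5.12 asks for a summary table with "descriptive statistics for PSA values at each cycle and the related percent change from baseline". It does not name the statistics for the percent change. It also calls for PSA outcomes for each patient and time point, and for listings of all PSA results.

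Section 3.4.1 includes "percent change in PSA from baseline to tumour assessment time point" among the tumour assessments. Per patient it is 100 × [1 − exp(ln(R))], where R is PSA at the cycle divided by baseline PSA. The same section says, for the maximum decline, that "a negative percent will indicate a decline in PSA".

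On group size, section 3.1 says "the first two cohorts will enroll 1 patient each" and "Cohorts of 3 patients will be enrolled from the 3rd cohort onwards", with expansion to 6 after a DLT. Section 4.1 groups patients by the dose actually received.

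**The concern.** The SAP recognises that PSA needs a log-scale summary and provides one for the PSA values. The variable that describes activity, the change from baseline, is defined on a scale where that summary cannot be computed. A programmer who follows the text is left with the arithmetic mean and SD, which section 4.1 sets aside for PSA, or must improvise.

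Percent change is bounded at 100% for a fall and unbounded for a rise. Its arithmetic mean in a small group therefore leans towards the largest riser. The same table would hold geometric means of PSA at each cycle, so two rows built from the same patients could point in opposite directions. Anti-tumour activity is a secondary objective, and PSA change is one of its few quantitative summaries.

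**Working it through.** **Inputs.** The definitions and group sizes come from SAP sections 3.1, 3.4.1, 4.1 and 5.12. The SAP gives no PSA data, mean or SD, so there is no figure of its own to reproduce, and all PSA ratios below are assumptions. A fall is counted as negative, as the text of 3.4.1 has it.

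**1. Does any log scale survive in the formula?** exp(ln(R)) = R, so the formula in 3.4.1 reduces to 100 × (1 − R) for each patient. No log scale reaches the group summary.

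**2. Can the 4.1 rule be applied to percent change?** A geometric mean needs ln of each value. For changes of −50% and −20%, ln(−50) and ln(−20) do not exist. Reversing the sign moves the problem to the patients who rise. The rule does work on R itself.

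**3. Three patients, R = 0.5, 0.8, 2.0.**
- Percent changes: −50, −20, +100.
- Arithmetic mean: (−50 − 20 + 100)/3 = +10.0%, SD 79.4.
- Geometric mean change: 100 × [(0.5 × 0.8 × 2.0)^(1/3) − 1] = 100 × (0.8^(1/3) − 1) = −7.2%.
- Median: −20%.

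**4. Varying the largest ratio (x).**

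| Other ratios | x | Arithmetic mean | Geometric mean change | Median |
|---|---|---|---|---|
| 0.5, 0.8 | 1.2 | −16.7% | −21.7% | −20% |
| 0.5, 0.8 | 2.0 | +10.0% | −7.2% | −20% |
| 0.5, 0.8 | 6.0 | +143.3% | +33.9% | −20% |
| 0.5, 0.7, 0.8, 0.9, 1.1 | 2.0 | 0.0% | −9.4% | −15% |
| 0.5, 0.7, 0.8, 0.9, 1.1 | 4.0 | +33.3% | +1.7% | −15% |
| 0.5, 0.7, 0.8, 0.9, 1.1 | 6.0 | +66.7% | +8.8% | −15% |

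Opposite signs occur over a limited range of x:
- In the group of three, the arithmetic mean is positive when x > 1.7, because 100(x − 1) must exceed 70. The geometric change is negative when 0.5 × 0.8 × x < 1, that is x < 2.5.
- In the group of six, the first five changes sum to −100, so the arithmetic mean is positive when x > 2.0. The product of the first five ratios is 0.2772, so the geometric change is negative when x < 1/0.2772 = 3.6.

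Above those ranges both means are positive, but the arithmetic one is several times larger.

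**5. How often?** Take log-normal ratios with no median change and log-SD s (assumed). The expected arithmetic mean is 100 × (exp(s²/2) − 1): about +5% for s = 0.3, +20% for 0.6 and +65% for 1.0. This does not shrink with group size. In a simulation of 200,000 groups per setting over that range of s, the arithmetic mean was positive while the geometric change was negative in 7% to 17% of groups of 3 and 12% to 29% of groups of 6.

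**6. Agreement with the PSA rows.** When the same patients contribute at both visits, geometric mean PSA at the cycle divided by geometric mean PSA at baseline equals exp(mean of ln R). The geometric mean change therefore always matches those rows. The arithmetic mean of percent change need not.

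**7. Sign as printed.** 100 × (1 − R) gives +50, +20 and −100 for the three patients in step 3, mean −10.0%. The text would read that as a decline. The geometric equivalent, 100 × (1 − 0.8^(1/3)), is +7.2%. The two summaries still conflict, but the direction is reversed.

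**The case against.** A reader might infer that the SAP prescribes an arithmetic mean of percent change. It does not write this. Section 5.12 says only descriptive statistics, and 4.1 names PSA as the case for the geometric option. The formula in 3.4.1 has the shape of a back-transformed log ratio, and with the mean log ratio inserted it would give the geometric mean change, apart from sign. The author may have meant that. Section 8 also points to a separate appendix that is not at hand and whose contents cannot be checked. This stands: the arithmetic mean is what a literal reading leaves, not a stated choice.

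A reader might also infer that the 4.1 rule cannot serve PSA change at all. That goes too far, since it works on the ratio.

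Nor do the documents support the idea that a conclusion of the trial would be distorted. The MTD/MAD rests on DLTs (6.1), and the response rate on the PCWG2 questions with an exact CI (4.5, 6.2.3). PSA change has no test or threshold. Median, minimum, maximum and patient listings are planned, so a single large riser would be visible. In one-patient groups the mean, the median and the geometric change coincide.

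These points limit the weight of the concern but do not remove it. The mean and SD would still be the statistics that the SAP's own rule replaces for PSA.

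**Conclusion.** The concern holds in a limited form. The SAP sets a log-scale rule for PSA and then asks for a summary of signed percent change, to which the rule cannot be applied, without saying what to use instead. Read literally, the arithmetic mean and SD apply. In groups of 3 to 6 patients one large rise can dominate that mean and can give it the opposite sign to the change in geometric mean PSA.

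The size rests on assumed ratios and log-SDs and on counting a fall as negative; under the printed formula the direction of the distortion reverses. Only the mean and SD of a descriptive secondary summary are affected. It is worth correcting because the correction is almost free and makes the change row agree with the PSA rows when the same patients contribute.

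**What to change.** In SAP sections 3.4.1 and 5.12:
- For each patient and cycle derive d = ln(PSA at cycle / baseline PSA).
- By dose group and cycle, report the geometric mean percent change, 100 × (exp(mean d) − 1), with geometric CV, 100 × √(exp(s²) − 1), where s is the SD of d. These replace the arithmetic mean and SD of percent change. In a one-patient group show the single value without a CV.
- Keep the planned median, minimum and maximum of the individual percent changes, and the listings. The geometric mean also responds to a very large rise (+33.9% against a median of −20% for ratios 0.5, 0.8, 6.0), so the median remains useful.
- Use one sign convention throughout, negative for a decline. The individual formula then becomes 100 × (exp(d) − 1).
- Use one baseline definition throughout. The formula in 3.4.1 takes the screening value, while the maximum-decline item in 3.4.1 and section 5.12 take Cycle 1 Day 1.

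The cost is one derived variable and a few lines of text, with no new data. The arithmetic mean percent change would no longer be shown.
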